will be derived for (a) the entire study, (b) the taper period, and (c) the post-taper period. These outcomes will be compared as a function of group and group x phase using independent groups t-tests and ANOVAs with Tukey post-hoc for pairwise comparisons. If data does not meet ANOVA assumptions, mixed model regressions will be used.

Secondary outcomes from the Sleep Profiler EEG may include measures of sleep continuity (sleep latency, sleep efficiency [total sleep time/time spent in bed], wake after onset [WASO], number of awakenings) and architecture (time spent in stage 1, stage 2, stage 3, and rapid eye movement [REM] sleep). (b) Secondary actigraphy outcomes may include wake after sleep onset (WASO), time spent napping, number of naps, and total activity. (c) Secondary self-report ratings may include subjective WASO, VAS sleepiness and quality of sleep, and Stanford Sleepiness Scale score. **Analyses:** All outcomes will be compared as a function of group (20mgSUVO, 40mg SUVO, and placebo) and phase (taper vs. post-taper), as well as group by day (7 nights) using 2-factor Proc Mixed analyses with Tukey posthoc testing. Area-under-the-curve (AUC) values for the entire study and the taper and post-taper periods will then be derived and compared as a function of group and group x phase using independent groups t-tests and ANOVAs with Tukey post-hoc for pairwise comparisons. If data does not meet ANOVA assumptions, mixed model regressions will be used.

Secondary actigraphy outcomes may include wake after sleep onset (WASO), time spent napping, number of naps, and total activity. Secondary self-report ratings may include subjective WASO, visual analogue scale (VAS) sleepiness and quality of sleep, and Stanford Sleepiness Scale score. All outcomes will be compared as a function of group (20mg SUVO, 40mg SUVO, and placebo) and phase (taper vs. post-taper), as well as group by day (7 nights) using area-under-the-curve (AUC). The taper and post-taper periods will then be derived and compared as a function of group and group x phase using independent groups t-tests and ANOVAs with Tukey post-hoc for pairwise comparisons. If data does not meet ANOVA assumptions, mixed model regressions will be used.

Secondary measures will be additional ratings on the hypothetical purchase task, SOWS and VAS ratings of opioid withdrawal, VAS ratings of abuse liability, self-reported craving, self-reported stress, perceived drug value, and diurnal salivary cortisol (measured via AUC values and mean daily cortisol) and cortisol/ACTH ratios. Purchase task data will be fit to opioid demand curves for comparison. **Analyses:** All outcomes will be compared as a function of group (20mg SUVO, 40mg SUVO, and placebo) and phase (taper vs. post-taper), as well as group by day (7 nights) using area-under-the-curve (AUC). The taper and post-taper periods will then be derived and compared as a function of group and group x phase using independent groups t-tests and ANOVAs with Tukey post-hoc for pairwise comparisons. If data does not meet ANOVA assumptions, mixed model regressions will be used. Exploratory analyses will include linear and multivariate regression models to examine the relationship between measures of sleep, stress, opioid withdrawal, and craving. Logistic regression will be used to examine the relationship between sleep, stress, opioid withdrawal, and craving on the likelihood of treatment attrition.

d. Early stopping rules.

Patients will discontinue their study participation if they request to be discharged, have a serious adverse event, or if the study physicians decide it is in the patient's best interest to be removed from the study. All patients will be discharged with naloxone, opioid overdose education, and referral to outpatient OUD treatment.

8. Risks

a. Medical risks, listing all procedures, their major and minor risks and expected frequency.

1. Risk associated with suvorexant (Belsomra®): Suvorexant is a Schedule IV dual orexin antagonist that is FDA-approved for the treatment of insomnia. Suvorexant is 82% bioavailable and has a Tmax of 2 hours. Tmax can be delayed by food though this does not impact the Cmax. It is extensively metabolized by the liver through CYP3A enzymes. The elimination half-life is 12 hours, and it is excreted through both renal (23% unchanged) and fecal (66%) means. Suvorexant is contraindicated with other CNS depressants and alcohol and strong CYP3A inhibitors. It is rated pregnancy category C, indicating insufficient data available to make determination for human subjects. Suvorexant is contraindicated in patients with narcolepsy, patients with recent suicidal behavior, or patients with severe hepatic impairment. There is no evidence of potential overdose and a toxic dose has not been established. Clinical trials that administered up to 240mg of suvorexant reported no overdose effects, though there was a dose-dependent increase in the frequency and duration of next day somnolence. As per product label, most common side effects are sleepiness/drowsiness (7% of people), headache (7%), dizziness (3%), diarrhea (2%), dry mouth (2%), upper respiratory infection (2%), abnormal dreams (2%), and cough (2%). Serious adverse effects include sleep paralysis (7%), somnolence (7%), and worsening of depression or suicidal ideation.

2. Risks associated with buprenorphine/naloxone: Participants in this study will be maintained on buprenorphine/ naloxone briefly before beginning a 4-day buprenorphine/naloxone taper. Buprenorphine is Schedule III FDA-approved medication that is approved for the indication of opioid withdrawal treatment. Participants in this study will receive the generic sublingual tablet version of this product (which also has naloxone). Buprenorphine is partial opioid agonist/antagonist at the opioid mu/kappa receptors (respectively), has a low ceiling on its agonist effects, and a slow dissociation from the receptors that results in a 26-hour elimination half-life. There is nothing experimental about the use of buprenorphine/naloxone use in this study. All participants will receive the same buprenorphine/naloxone detoxification schedule, and the highest potential dose (24mg) is well below what can be administered for use on a daily basis (32mg). Buprenorphine/naloxone has very few contraindications, and is not recommended for patients with respiratory distress (such as acute or severe bronchial asthma, or respiratory depression), patients with a known allergy to buprenorphine, or patients with history of cardiac problems such as long QT syndrome or severe hypotension. It is contraindicated for use with the opioid antagonist naltrexone or other opioid agonists. It is rated in pregnancy category C, therefore all women who are pregnant or breastfeeding will be excluded from study participation. Buprenorphine/naloxone's noted side effects are minimal and rare (hyperhidrosis 14%, abdominal pain 11%, constipation 12%, nausea 15%, headache 37%, insomnia 14%) and overlap significantly with known opioid withdrawal symptoms (e.g., abdominal pain, nausea).

3. Risk associated with opioid withdrawal: It is expected that participants will experience some level of opioid withdrawal as part of this study. Symptoms of opioid withdrawal include nausea, diarrhea or stomach cramping, muscle aches and pains, yawning, sweating, pupil dilation, minor increases in blood pressure, and runny nose/tearing eyes.

4. Risk of opioid overdose: Patients are at an increased risk of experiencing an opioid overdose whenever their tolerance to opioids has decreased. This includes completion of an opioid detoxification (or leaving prison/jail). The reason for this increased risk is really related to patient knowledge of how their tolerance contributes to their opioid use, and patients who are not aware that their tolerance has decreased and relapse to opioids by using the same dose they were using before they entered treatment are most susceptible to an opioid-related overdose. 5. Risk associated with clonidine: Patients may receive clonidine during the induction period only to assist with the transition from illicit opioids to buprenorphine/naloxone. Clonidine will be administered per clinical recommendation and this study expects to use it in only a very small number of patients. The largest risk associated with clonidine is hypotension (experienced in 44.8% of patients). Up to 38% of patients may also experience symptoms related to sedation, fatigue, and/or. Fewer than 10% of patients experience symptoms related to GI upset (nausea, constipation), insomnia, respiratory, neurologic, or psychiatric complications. Clonidine has few contraindications, however given that it

reduces blood pressure will not be administered to participants whose blood pressure is <80/60, however we expect this to be rare because hypertension is a symptom of opioid withdrawal.

b. Steps taken to minimize the risks.

Adverse events will be assessed daily. The safety of participants is a priority of our research unit. The largest potential risks to participants on SUVO are worsening of depression and/or sleep paralysis. We will exclude any participant with current major depressive disorder, past year suicidal behavior, or self-reports of current sleep paralysis. Medical team members will be consulted about adverse events and we will follow all reporting guidelines. In the event of an SAE, appropriate courses of action may include observing the participant until the parameters return to normal or transferring the participant to the Emergency Department (ED). Our research unit, the location in which all study sessions will be conducted, is located across the street from the Johns Hopkins Bayview Medical Center (JHBMC) ED. Participants who can walk will be escorted to the ED by a study staff member. If there is any question in a participant's ability to walk safely then 911 will be called to have an ambulance dispatched for the participant.

Given the small sample size, the relatively short study duration, and the fact that medications are being administered as clinically-indicated, we are not planning an interim analysis.

c. Plan for reporting unanticipated problems or study deviations.

Adverse events may be identified by a member of the research staff, the Principal Investigators, or study co-investigators. The PI will be responsible for consulting a medical team member about adverse events. The PI and research staff will meet on a weekly basis to review safety monitoring data and adverse events and to ensure that any safety concern has been addressed by medical staff and has been recorded appropriately.

All SAEs will be reported to the JHM IRB within 3 working days after a study PI learns of the event. In addition, the study PI will notify the study co-investigators, the NIDA Program Official, and the FDA (if applicable). The PI will coordinate dissemination of subsequent information obtained relating to the death (e.g., autopsy report, hospital records, toxicological analyses).

The Johns Hopkins IRB will be provided with an annual summary of AEs and SAEs as part of the continuing review. If any SAEs requires a change to the protocol or consent form, the PI will make those changes promptly and submit the revised documents to the JHM IRB and appropriate other agencies.

Important adverse events that are unanticipated, including pregnancy, will be reported to the Johns Hopkins IRB within 10 working days. If the important adverse events requires changes to the protocol or consent form, the PI will make those changes promptly and submit the revised documents to the IRB and appropriate other agencies.

d. Legal risks such as the risks that would be associated with breach of confidentiality.

Information about study subjects will be kept confidential and managed according to the requirements of the Health Insurance Portability and Accountability Act of 1996 (HIPAA). Consistent with these regulations a signed authorization will be obtained that informs each subject of the following:

- What protected health information (PHI) will be collected from subjects in this study
- Who will have access to that information and why
- Who will use or disclose that information
- The rights of a research subject to revoke their authorization for use of their PHI.

In the event that a subject revokes authorization to collect or use PHI, the investigator, by regulation, retains the ability to use all information collected prior to the revocation of subject authorization. For subjects that have revoked authorization to collect or use PHI, attempts should be made to obtain permission to collect at least vital status (i.e. that the subject is alive) at the end of their scheduled study period.

e. Financial risks to the participants.

There are no financial risks to the patient.

9. Benefits

a. Description of the probable benefits for the participant and for society.

This study will increase our understanding of the association between sleep and opioid withdrawal symptoms, the degree to which sleep impairment contributes to opioid treatment outcomes, and the degree to which a novel FDA-approved medication (suvorexant) with low abuse liability, high safety profile, and immediate onset of action has on sleep impairment during opioid withdrawal. This will be the first study to examine this medication in opioid use disorder (OUD) patients, the first to examine any sleep pharmacotherapy with OUD patients during a withdrawal procedure, and the first to use a rigorous unobtrusive, wireless, objective EEG monitor to collect sensitive objective data regarding sleep continuity and architecture. These results will be rigorous and transparent and will advance our understanding of the role sleep may play in OUD and the value of evaluating the orexin system’s role in OUD more broadly, to ultimately provide an empirically-supported way to address the opioid epidemic.

10. Payment and Remuneration

a. Participants will earn \$30 for the screening visit. Participants who complete the study will earn \$100 per day for a total of \$1100. Participants will also earn an adherence bonus of \$30/day (up to \$300) for wearing the wireless EEG device throughout the night. The total maximum payment is \$1430 (See Payment Table).

Payment Schedule		
	Daily Payments	EEG Bonus
Screen	\$30	-
Day 1	\$100	-
Day 2	\$100	\$30
Day 3	\$100	\$30
Day 4	\$100	\$30
Day 5	\$100	\$30
Day 6	\$100	\$30
Day 7	\$100	\$30
Day 8	\$100	\$30
Day 9	\$100	\$30
Day 10	\$100	\$30
Day 11	\$100	\$30
Follow-up	\$30	-
Total	\$1160	\$300
Maximum Payment	\$1460	

11. Costs

- a. Detail costs of study procedure(s) or drug (s) or substance(s) to participants and identify who will pay for them.

The participants in this study will not pay for any aspect of study participation. All study medications, residential treatment costs, and staff support is paid through the NIHA grant **UG3DA048734-01**.

References

- Aston, E. R., Metrik, J., & MacKillop, J. (2015). Further validation of a marijuana purchase task. *Drug and Alcohol Dependence, 152*, 32-38.
- Bunce, S. C., Harris, J. D., Bixler, E. O., Taylor, M., Muelly, E., Deneke, E., . . . Meyer, R. E. (2015). Possible evidence for re-regulation of HPA axis and brain reward systems over time in treatment in prescription opioid-dependent patients. *Journal of Addiction Medicine, 9*(1), 53-60. doi:10.1097/ADM.0000000000000087 [doi]

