Screening Visits: Participants will be recruited from the community via flyers, newspaper postings, and other media outlets. Screening visits will take place on the Behavioral Pharmacology Research Unit at the Johns Hopkins Bayview Medical Center. Individuals will complete a phone-screen to assess for initial eligibility and will be invited for a clinic-based visit to confirm final eligibility. During this visit, participants will first review an informed consent form with a staff member and discuss the study before

providing voluntary informed consent to participate. Participants will then complete a series of measures to establish study eligibility, including a demographics questionnaire, self-reported opioid use and withdrawal, a past 30-day timeline follow back for drug and alcohol use, assessments of DSM-5 drug and alcohol use disorders, the Stop-Bang questionnaire assessment of sleep apnea, psychiatric functioning (MINI International Neuropsychiatric Interview [Sheehan et al., 1998]), and the Columbia Suicide Severity Rating Scale (Posner et al., 2011). Participants will provide a blood sample that will be tested for complete blood count and comprehensive metabolic panel, provide a urine sample that will be tested for evidence of opioid and other drug use, and pregnancy (when applicable). Either during the Screening or admission day, participants will complete a medical history and physical examination with qualified medical staff to determine final study eligibility. The physical examination will include an electrocardiogram (ECG) to determine if the participant has any heart abnormalities, and the Brief Pain Inventory to quantify current chronic pain issues (Cleeland et al., 1994). Opioid withdrawal scales will be collected at the end of the Screening visit to help confirm opioid physical dependence.

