Buprenorphine Induction and Stabilization: Participants will be inducted onto buprenorphine prior to beginning the buprenorphine taper. Induction may occur up to 3 weeks prior to admission to the CRU. Participants will be required to show evidence of opioid withdrawal (as per ratings on the COWS) and will receive incremental doses of buprenorphine throughout the day, up to a maximum of 16mg of buprenorphine on the induction day. The induction protocol will be conducted as clinically indicated, based upon medical team recommendations. To increase comfort during the induction, the medical team may administer the PRN concomitant medications that are approved for the taper protocol as well as clonidine. Participants may then be maintained on buprenorphine as an outpatient for up to 3 weeks before CRU admission. Briefly maintaining participants on buprenorphine will enable the study to retain participants between Screening and CRU admission, as the CRU has restricted access for protocols requiring weekend coverage. Participants who are maintained on buprenorphine as an outpatient will receive blister packages of sublingual buprenorphine for outpatient administration and may receive up to 24mg/day (beginning the day after induction) during this period. During the stabilization period between Screening and Admission, participants will be required to visit the clinic on a weekly basis to exchange blister packages. Participants may receive assistance (e.g., bus tokens) from the study to help facilitate transportation to the BPRU on those days. Any participant receiving >16 mg as an outpatient will be transitioned to 16mg on the CRU admission day. Participants who are inducted onto buprenorphine on the CRU admission day will follow an identical induction procedure and will only receive up to 16mg.

Clinical Research Unit (CRU): Following confirmation of eligibility, participants will be admitted onto a residential CRU that is located on the Bayview Medical Campus. Participants will reside on the CRU for up to 11 days (10 nights) and will be allowed to smoke cigarettes ad libitum in a designated smoking area during their stay. Female participants will provide a sample of blood upon admission that will be analyzed for levels of progesterone and estrogen.

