Stress and Craving Measures: Several brief and validated measures (such as those below) will be used to inform potential mechanism underlying effects and whether prospective studies to examine these effects more thoroughly are warranted.

1. *Visual Analog Ratings*: Self-report ratings of opioid craving (e.g. How much do you want to use right now? How much do you want to avoid using right now? How much control would you have over using if someone offered you opioids right now?) and stress (e.g. How stressed do you feel right now? How much is opioid withdrawal contributing to your stress?)
2. *Diurnal Cortisol*: Salivary cortisol will be collected several times daily. Diurnal cortisol is a measure of HPA-axis function that affects the sleep-wake cycle (Edwards, Evans, Hucklebridge, & Clow, 2001) .
3. *Additional HPA-axis Measures*: One blood sample will be taken during the stabilization, withdrawal, and post-withdrawal periods to measure change in adrenocorticotrophic hormone to cortisol ratios. These measures have been associated with treatment outcomes in other substance using populations including cocaine use disorder (Sinha, Garcia, Paliwal, Kreek, & Rounsaville, 2006) .

b. Study duration and number of study visits required of research participants.

The entire study will consist of one screening visit and a residential stay over the course of 11 days and 10 nights. All study activities will take place at the BPRU and the Bayview CRU.

c. Blinding, including justification for blinding or not blinding the trial, if applicable.

The only blinded medication in this study is SUVO. Since this is the medication of interest, participants will be blinded to ensure study rigor and assess the utility of SUVO to treat sleep disturbance compared to placebo. The buprenorphine taper and concomitant medications will not be blinded in order to mimic the real-world experience of supervised opioid withdrawal and increase ecological validity.

d. Justification of why participants will not receive routine care or will have current therapy stopped.

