- Have no clinically significant chronic medical or surgical disorders or conditions that are judged by the investigators to prevent participation.

Exclusion Criteria:

- Seeking or currently enrolled in methadone or buprenorphine maintenance treatment for OUD
- Pregnant or breast feeding.
- Have evidence of physical dependence on alcohol or benzodiazepines that requires medical detoxification.
- Have a known allergy to the study medications.
- Past 30-day prescribed use of suvorexant or benzodiazepines for the indication of insomnia.
- Current use of an SSRI or MAO inhibitor for depression or insomnia, or other medications that are contraindicated with suvorexant.
- Current narcolepsy, restless leg syndrome, or sleep paralysis.
- High risk for current sleep apnea as assessed via the Stop Bang questionnaire.
- Current major depressive disorder.
- Past year suicidal behavior as assessed via the Columbia Suicide Severity Rating Scale
- Severe hepatic or renal impairment, defined as:
 - AST or ALT $>3x$ ULN.
 - Total Bilirubin $>2x$ ULN.
 - Creatinine $>1.5x$ ULN.
- Have circumstances that would interfere with study participation (e.g., impending jail).

6. Drugs/ Substances/ Devices

- a. The rationale for choosing the drug and dose or for choosing the device to be used.

Suvorexant (SUVO): SUVO is FDA-approved for the treatment of insomnia and is an ideal candidate for evaluation because it is intended for PRN administration, improves sleep architecture after a single dose (Herring et al., 2016b; Sun et al., 2013), and does not cause a withdrawal syndrome after abrupt discontinuation even when it has been administered chronically for several weeks (Herring et al., 2016b). This study utilizes two doses of SUVO (20 and 40mg) to evaluate which dose has a superior risk/benefit profile, although we do not anticipate a high rate of adverse events for either dose. The most effective dose can then be used in future clinical trials as well as in practice for the treatment of sleep disturbance during opioid withdrawal. Participants will be given their medication dose in two weight and color-matched capsules, containing either two 20mg SUVO (40mg dose), two 10mg SUVO (20mg dose), or two placebo capsules. As an added precaution, participants will be allowed to reduce their dose from two to one capsule (representing a 50% dose decrease) if they experience negative side-effects and would prefer a lower dose.

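### Pregnancy is an exclusion, but the plan specifies a test only at screening, and suvorexant can start 23 or more days later

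*Combined protocol and SAP*

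**What the plan says.** The exclusion is clear. The list in Section 5 includes "Pregnant or breast feeding". Section 8.a, item 2, gives buprenorphine/naloxone's pregnancy category C as the reason, "therefore all women who are pregnant or breastfeeding will be excluded from study participation". Section 8.a, item 1, gives suvorexant the same category and explains that the human data are too few for a determination.

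The check on that exclusion is in Section 4.a, Screening Visits, where participants "provide a urine sample that will be tested for evidence of opioid and other drug use, and pregnancy (when applicable"). Section 4.b counts one such visit: "The entire study will consist of one screening visit and a residential stay over the course of 11 days and 10 nights".

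The timing comes from several places:

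- Section 4.a, Buprenorphine Induction and Stabilization: "Induction may occur up to 3 weeks prior to admission to the CRU", and "Participants may then be maintained on buprenorphine as an outpatient for up to 3 weeks before CRU admission".
- Section 6.a, Buprenorphine: three days of stabilization, then a four-day taper.
- Section 4.a, Study Medications: blinded dosing begins on the night preceding the first taper day.
- Section 4.a, Post-taper Phase: four further days.

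At admission, Section 4.a (Clinical Research Unit) adds one procedure for women: "Female participants will provide a sample of blood upon admission that will be analyzed for levels of progesterone and estrogen".

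**The concern.** The exclusion is meant to keep pregnant women from receiving study drug, but the only specified test can be weeks old when dosing starts. During those weeks participants live in the community, and Section 5 has no contraception requirement. Two groups of women would pass: those whose pregnancy was too early to show at screening, and those who conceived during the outpatient period.

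The long path is a planned one. Section 4.a explains that outpatient maintenance exists because access to the residential unit is restricted. Women are expected, since sex is one of the four minimisation factors.

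What is at stake is participant protection. A woman in either group could receive suvorexant at 40 mg, above the 10 mg and 20 mg doses that Section 6.b gives as approved, and would also undergo the taper. The plan has no later test that would reveal the exposure: the follow-up urine is described only for illicit drug use. Section 8.c provides for reporting a pregnancy to the IRB within 10 working days, but that applies after the fact.

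**Working it through.** This is a calendar count; no power or sample-size formula is involved.

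**Step 1: reproduce the plan's length of stay.** Stabilization is 3 days (Section 6.a), taper 4 days and post-taper 4 days (both Section 4.a).

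3 + 4 + 4 = 11 days, hence 10 nights.

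This matches the stated stay of 11 days and 10 nights, so the admission day is stabilization day 1.

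**Step 2: place the first dose.** Dosing starts on the evening of stabilization day 3, which is admission day + 2.

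**Step 3: interval from test to first dose.** Let *g* be the days from screening to induction and *w* the days from induction to admission. The plan allows *w* from 0 to 21 and states no limit on *g*.

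Interval = *g* + *w* + 2

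| Path | *g* | *w* | Days from test to first dose |
|---|---|---|---|
| Screening, induction and admission on one day | 0 | 0 | 2 |
| Induction on the screening day, full outpatient period | 0 | 21 | 23 |
| As above, induction 7 days after screening (assumed) | 7 | 21 | 30 |
| As above, induction 14 days after screening (assumed) | 14 | 21 | 37 |

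If the admission day were not counted as stabilization day 1, the second row would be 24, but that does not fit the 11-day stay.

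**Step 4: look for a later test.** Each point after screening was checked in the text.

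- *Induction and weekly outpatient visits (Section 4.a):* the stated purpose of the weekly visits is to exchange blister packs. No pregnancy test is listed.
- *History and physical (Section 4.a, Screening Visits):* these may be done at screening or on the admission day. The named components are an ECG and the Brief Pain Inventory.
- *Admission (Section 4.a):* it follows confirmation of eligibility, but no repeat test is named. The women's blood sample is for two hormones, with no eligibility rule attached.
- *Randomisation and dosing (Section 4.a):* no test is listed.
- *Risk minimisation (Section 8.b):* it covers depression, suicidal behaviour and sleep paralysis, and does not mention pregnancy.

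**Step 5: effect of a test at admission.** The longest interval falls from at least 23 days to 2. A test on the day of the first dose, before randomisation, would bring it to 0.

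**The case against.** The strongest reply is that the claim rests on silence. The protocol never says that screening is the only time pregnancy is tested. The eligibility examination may fall on the admission day, its listed contents need not be exhaustive, and the site may test at admission as routine. This stands as far as it goes: the accurate statement is that no repeat test is specified, not that none will be done. It does not close the gap, because a site following the text need not retest anyone.

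A second reply is that 23 days describes only participants who use the whole outpatient allowance. The protocol speaks of stabilization between screening and admission, which can be read as making the outpatient period and the screening-to-admission interval the same thing. On that reading 23 days is about the longest case, and the 30- and 37-day figures rest on assumed values. This is fair. The documents set no limit either way, and they do not say how many participants will use the full period.

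Third, a test at admission does nothing about buprenorphine already taken as an outpatient. That is correct. The benefit is limited to suvorexant and the taper. The statement about insufficient human data is also made for suvorexant only; for buprenorphine/naloxone the protocol gives just the category.

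Finally, the point touches no endpoint, power calculation or analysis. That is true, and it is offered as a participant-safety point.

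**Conclusion.** The concern holds. Followed as written, the plan can randomise and dose a pregnant woman against its own exclusion. The interval between the only specified test and the first suvorexant dose is 23 days on the full outpatient path with induction on the screening day. It is longer if screening comes earlier, and can be as short as 2 days for someone screened, inducted and admitted together.

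The count assumes that the admission day is stabilization day 1, which the 11-day stay supports. The size given is a time gap and not a risk: the documents give neither the expected number of women nor the share using the outpatient route, so the number of exposures cannot be estimated and may be small. The change should still be made, because it is cheap and enforces a rule the sponsor has already set.

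**What to change.** Add one sentence to Section 4.a (Clinical Research Unit) and to Section 5: a negative pregnancy test at admission to the residential unit is required before randomisation, where applicable. It can be an hCG assay on the blood already drawn from women that day, or a urine dip. State that a positive result excludes the participant from randomisation, and that care afterwards is for the medical team. If the site already tests at admission, the sentence simply records it.

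The cost is one assay for each woman among the planned 45 participants, on a sample already taken or a simple urine specimen, with no added visit. The documents give no prices, so describing this as low-cost is a judgement. The drawback is an occasional exclusion after outpatient buprenorphine and a unit bed have been used. Because it would come before randomisation, it would remove no one from the randomised comparison. Some residual risk remains, since a very early pregnancy could also be missed at admission.
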